8. EFFICACY ASSESSMENTS

8.1. Sputum Culture

Microbiological assessment of sputum specimens will be used for secondary efficacy measurements.

During the study, pre-dose expectorated or induced sputum samples (approximately 2 mL) are required at study visits specified in the Schedule of Assessments (Table 4). To improve the probability of obtaining a good sputum specimen, 2 sputum samples will be obtained from each subject at each assessment; subjects will provide 1 sputum sample on the day prior to the scheduled visit, and 1 sputum sample on the day of the visit prior to dosing with study drugs. At Screening, subjects will provide 1 sputum sample on the day of the visit and 1 sputum during the week following the Screening visit. If a subject is unable to produce sputum spontaneously, sputum may be induced. If after induction, a subject is still unable to produce sputum despite reasonable efforts, this will be recorded as non-productive at that time point. It is recommended to schedule an in-clinic visit as a backup to non in-clinic visits in case the subject is not able to spontaneously produce sputum at home. If a subject is unable to spontaneously produce sputum at home on the day prior to the scheduled visit, the subject should then come into the clinic for sputum induction on the scheduled visit. The induction should be performed within the specified visit window (Table 4). At the scheduled visit, once sputum is collected (spontaneously or by induction), study drugs can be administered. If the subject produces their best sputum samples first thing in the morning prior to being able to attend a clinic visit, the subject should consistently collect sputum samples first, then proceed with PRO assessments and other assessments throughout the study.

Sterile, leak proof, non-wax, disposable plastic containers labeled with 2 subject identifiers will be used to collect specimens aseptically to avoid contamination. Sputum samples should be refrigerated, not frozen, until shipped to the central microbiology laboratory as soon as possible to avoid overgrowth by contaminating normal flora. No fixative or preservatives are to be used with sputum samples. Detailed instructions for collecting, processing, and shipping sputum specimens will be provided in the site laboratory manual. Subjects will be provided with instructions for collecting, processing, and shipping sputum specimens for samples collected at non in-clinic visits.

Sites are strongly discouraged from performing local mycobacterium sputum cultures for the duration of the study, as this may introduce bias to subject assessments. Sputum may be sent to local laboratories to be cultured for organisms other than mycobacterium.

Microbiological Assessment

Sputum specimens will be cultured in broth media (liquid) in addition to agar media (solid), and will be held for up to 6 weeks. A negative culture result will not be reported until after this time has transpired. All contaminated samples will be retreated and re-cultured once.

Growth of other bacteria due to co-infections (eg, *Pseudomonas aeruginosa*, *M. abscessus*, other NTM) will be reported as applicable. Colony counts of MAC growth will be reported. Isolates of MAC will be identified using a commercial RNA probe (AccuProbe, Gen Probe, Inc., GenoType NTM-DR Ver 1.0, Hain Lifescience) and subsequently identified to species using molecular

methodology (Cousins et al., 1996). Standard antibiotic sensitivity testing using MICs will be routinely performed on mycobacterial isolates (CLSI, 2018a; CLSI, 2018b; Forbes et al., 2008).

The MAC species and genotype at the Screening and/or Baseline sputum specimen will be identified by whole genome sequencing (Illumina Nextseq500TM) in subjects who achieve sputum culture conversion and who subsequently have positive sputum culture(s) (broth or agar); typing by whole genome sequencing will also be conducted.

MAC Culture Assessment Definitions

MAC culture negative	No MAC growth on agar media and broth media in all sputum cultures at a visit.
Non-productive	Prior to culture conversion or post recurrence: visits where subjects were recorded as non-productive are considered MAC culture positive. Post culture conversion: visits where subjects were recorded as non-productive are considered MAC culture negative.
Culture conversion	No MAC growth on agar media and broth media in all sputum cultures at 2 consecutive visits. The date of conversion is defined by the date of the first of 2 consecutive negative cultures.
Recurrence: Relapse	Subsequent to culture conversion, at least 1 MAC positive culture in agar media or positive cultures in broth media in at least 2 consecutive visits. A MAC positive culture is defined as the same species and genome as cultured at Screening/Baseline.
Recurrence: New infection	Subsequent to culture conversion, at least 1 MAC positive culture in agar media or positive cultures in broth media in at least 2 consecutive visits. A MAC positive culture is defined as a culture that is different than cultured at Screening/Baseline (different species, or same species but different genome).

8.2. Actigraphy

The Philips Actiwatch Spectrum PRO actigraphy device resembles a wristwatch and senses the activity of the wearer. It is to be worn continuously by the subject throughout the duration of the study. It is water-resistant and does not need to be removed for bathing. The subject will be provided with charging materials and should be instructed to charge the device once every 30 days (if needed). The data collected should be downloaded at each in-clinic visit or during a home care visit (if applicable).

9. SAFETY ASSESSMENTS

9.1. Vital Signs and Pulse Oximetry

Systolic and diastolic BP, pulse rate, body temperature, RR, and oxygen saturation will be recorded in the eCRF at study visits specified in the Schedule of Assessments (Table 4).

9.2. Physical Examination

A physical examination of the head (external), eyes, ears, nose and throat, lungs, cardiovascular system, abdomen, musculoskeletal system, skin, lymph nodes, central nervous system, and, as appropriate, other body systems will be performed at study visits specified in the Schedule of Assessments (Table 4). The physical examination will also include measurement of body weight. The measurement of height, without shoes, will only be done at Screening. Any abnormalities noticed at Screening will be recorded as medical history or as AEs if they occurred after randomization.

9.3. Audiology Test

Audiology testing will be performed at study visits specified in the Schedule of Assessments (Table 4). Additional assessments may be conducted if required per local labeling guidance. Frequencies of 250, 500, 1000, 2000, 4000, and 8000 Hz will be evaluated for each ear using air conduction.

9.4. Forced Expiratory Volume in 1 Second (FEV₁)

FEV₁ will be performed by trained personnel at the site and will be based on local assessments. Spirometers will be provided if not available at the study sites. FEV₁ will be performed (prior to bronchodilator use if applicable) at Screening and Day 1/Baseline (Table 4) prior to the administration of study drugs.

9.5. ECG Monitoring

ECG monitoring should be performed if required by local labeling guidance to monitor QT/QTc. In the event of QT/QTc interval prolongation, monitoring should continue until QTcF returns to normal range for the subject. Investigators should manage subject per local labeling guidance.

9.6. Ophthalmologic Test

Ophthalmologic tests (eg, visual acuity, visual field, color vision and fundus) should be performed if required by local labeling guidance. Investigators should manage subjects per local labeling guidance.

9.7. Clinical Laboratory Evaluations

Clinical laboratory tests of hematology, blood chemistry, and urinalysis will be performed via the study designated laboratory at study visits specified in the Schedule of Assessments (Table 4). The clinical laboratory test parameters are listed in Table 5. Laboratory assessments will not be performed at Month 5 (Visit 7).

Mid-stream clean catch urine samples will be collected for urinalysis. Urine dipsticks will be used for urine pregnancy testing. The clinical laboratory test parameters are listed in [Table 5](#).

Instructions for collection, storage, and shipment of clinical laboratory samples will be provided in the clinical laboratory manual provided in the site study binder.

Table 5 Clinical Laboratory Parameters

Clinical chemistry	Sodium, chloride, potassium, CO ₂ , magnesium, calcium, glucose, phosphate, total bilirubin (with direct and indirect fractionation, if total bilirubin is elevated ≥ 2 ULN), alkaline phosphatase, LDH, AST, ALT, albumin, total protein, creatinine, urea-nitrogen, uric acid, estimated glomerular filtration rate from the Cockcroft-Gault method
Hematology	Hemoglobin, erythrocytes, hematocrit, MCH, MCV, MCHC, leukocytes, differential blood count of neutrophils, eosinophils, basophils, monocytes, lymphocytes, and platelets
Urinalysis	Qualitative analysis of glucose, ketones, nitrites, protein, pH, leukocytes, blood, bilirubin, specific gravity; microscopic examination for cells, casts, and bacteria

ALT = alanine aminotransferase; AST = aspartate aminotransferase; CO₂ = bicarbonate; LDH = lactate dehydrogenase; MCH = mean corpuscular hemoglobin; MCHC = mean corpuscular hemoglobin concentration; MCV = mean corpuscular volume; ULN = upper limit of normal.

C-reactive protein

Blood samples will be drawn at study visits specified in the Schedule of Assessments ([Table 4](#)) to measure the concentration of CRP.

Pregnancy Test

A serum pregnancy test will be performed on WOCBP at Screening. A urine pregnancy test (at least 25 mIU/mL sensitivity) will be performed on WOCBP as specified in the Schedule of Assessments ([Table 4](#)). Results will be entered into the eCRF. Women not of childbearing potential are defined as postmenopausal (ie, amenorrheic for at least 12 months), or surgically or naturally sterile.

9.8. Chest CT Scan

A chest CT scan will be performed at Screening. A prior chest CT scan may be used if this CT scan was obtained within 6 months from the subject’s Screening visit. Chest CT scan will be read locally.

9.9. Adverse Events

The Investigator is responsible for detecting, documenting, and recording events that meet the definition of an AE or SAE as provided in the protocol and remain responsible for following up all AEs.

The Investigator should proactively follow subjects with AEs until the EOS for each subject. At the EOS visit, the Investigator will record the AE status in the eCRF.

9.9.1. Definition of an Adverse Event

An AE is defined as any untoward medical occurrence in a subject or clinical investigation subject administered a pharmaceutical product and which does not necessarily have to have a causal relationship with this treatment. An AE can therefore be any unfavorable and unintended sign (including an abnormal laboratory finding, for example), symptom, or disease temporally associated with the use of a medicinal product, whether or not considered related to the medicinal product.

Medical occurrences that begin after obtaining informed consent, but before administration of study drugs will be recorded under medical history/Current Medical conditions, not as AEs.

Treatment-emergent adverse events are AEs that occurred on or after the date of first dose of study drugs and within 28 days after the end of treatment.

It is the responsibility of Investigators, based on their knowledge and experience, to determine, those circumstances or abnormal laboratory findings which should be considered adverse events.

9.9.2. Definition of a Serious Adverse Event

An SAE is any untoward medical occurrence that at any dose:

- Results in death,
- Is life-threatening,
- Requires inpatient hospitalization or prolongation of existing hospitalization,
- Results in persistent or significant disability/incapacity,
- Is a congenital anomaly/birth defect, or
- Is an important medical event.

Note: The term “life-threatening” in the definition of “serious” refers to an event in which the subject was at risk of death at the time of the event; it does not refer to an event which hypothetically might have caused death if it were more severe (ICH E2A Guideline. Clinical Safety Data Management: Definitions and Standards for Expedited Reporting, October 1994).

Medical and scientific judgment should be exercised in deciding whether expedited reporting is appropriate in other situations, such as important medical events that may not be immediately life-threatening or result in death or hospitalization but may jeopardize the subject or may require intervention to prevent one of the other outcomes listed in the definition above. Examples include allergic bronchospasm, convulsions, and blood dyscrasias or development of drug dependency or drug abuse.

Note:

- A procedure is not an AE or SAE, but the reason for the procedure may be an AE or SAE.
- Pre-planned (prior to signing the ICF) procedures or treatment requiring hospitalizations for pre-existing conditions which do not worsen in severity are not SAEs.

- Suspected transmission of an infectious agent via a medicinal product should be considered as a SAE
- Laboratory abnormalities are usually not recorded as AEs or SAEs. However, abnormal laboratory findings (such as clinical chemistry, hematology, or urinalysis) or other abnormal assessments (physiologic tests such as electrocardiograms [ECG], imaging studies, or vital signs) that are associated with signs and/or symptoms, or are considered clinically significant in the judgment of the Investigator, require therapeutic intervention, or lead to discontinuation of the administration of study drugs, must be recorded as AEs or SAEs if they meet the definitions of an AE (or SAE).

9.9.3. Adverse Events of Special Interest

Adverse events of special interest are defined as events known to be attributed to parenteral amikacin and inhalation of antibiotics. Additional information on some AESIs will be collected in the eCRF. The AESI category groups and preferred terms include the following:

- Hypersensitivity pneumonitis (allergic alveolitis, pneumonitis, interstitial lung disease)
- Hemoptysis (hemoptysis)
- Bronchospasm (asthma, bronchial hyperreactivity, bronchospasm, dyspnea, exertional dyspnea, prolonged expiration, throat tightness, and wheezing)
- Exacerbation of underlying pulmonary disease (COPD, infective exacerbation of chronic obstructive pulmonary disease, and infective exacerbation of bronchiectasis)
 - Pulmonary exacerbation will be defined based on the Investigators best clinical judgment. Details of these events should be reported in an additional “pulmonary exacerbation” page of the eCRF.
- Ototoxicity (deafness, neurosensory deafness, unilateral deafness, dizziness, hypoacusis, presyncope, tinnitus, vertigo)
- Nephrotoxicity (nephropathy toxic, azotemia, oliguria, albuminuria, acute kidney injury, anuria, renal impairment)
- Neuromuscular disorders (muscle weakness, peripheral neuropathy, and balance disorder)

9.9.4. Assessment of Severity

The following definitions should be used to assess intensity of AEs:

- Mild: Awareness of sign or symptom, but easily tolerated, ie, does not interfere with subject’s usual function.
- Moderate: Discomfort enough to cause interference with usual activity.
- Severe: Incapacitating with inability to work or do usual activity, ie, interferes significantly with subject’s usual function.

9.9.5. Assessment of Causality

The Investigator who identifies an AE will determine the causality of each based on the temporal relationship to administration of study drugs and clinical judgment. The degree of certainty about causality will be graded using the categories listed below.

- **Related:** A reaction that follows a reasonable temporal sequence from administration of study drugs; that follows a known or expected response pattern to the study drugs; that disappears or decreases on cessation or reduction in study drugs dose; and/or that reappears or worsens when the study drugs is administered. Could not be reasonably explained by other factors such as underlying disease, complications, concomitant drugs, or concurrent treatments.
- **Not Related:** A reaction for which sufficient data exist to indicate that the etiology is unrelated to the study drugs.

9.9.6. Management of Adverse Events

Initial education of adverse effect expectations is crucial for subjects initiating study drugs in order to maintain retention of subjects in the study. Based on data from the ALIS development program, there is an association with ALIS and respiratory symptoms (eg, cough, dyspnea) reported as AEs, likely from airway irritation by the inhaled antibiotic. Data observed from Study INS-212 (refractory MAC population) show that the majority of subjects treated with ALIS experienced their first AE within 60 days of initiating ALIS. Azithromycin may cause gastrointestinal symptoms. Subjects should be monitored for visual acuity when taking ethambutol.

Data have shown that specific interventions may be helpful in the management of TEAEs ([Swenson et al., 2020](#)). Pretreatment with a bronchodilator, move administration of ALIS to the evening, antitussives, post-dose gargle (warm liquid or glycerin), and other interventions may help with management of TEAEs.

9.10. Reporting Requirements

9.10.1. Adverse Events

All AEs will be reported on the Adverse Events Form of the eCRF. Adverse events that occur between the time subject signs the ICF for the study and the time when subject receives his/her first dose of study drugs on Day 1 will be summarized as medical history and not as a TEAE unless the event meets the definition of an SAE as defined above. Additional information on some AEs will be collected in the eCRF.

9.10.2. Serious Adverse Events

All SAEs, regardless of causality, must be reported to organization delegated by the Sponsor on an SAE Report Form within 24 hours of becoming aware of the event; corrections and additions are required to be submitted within 24 hours. Study-specific email, telephone, and fax number for SAE reporting are presented in the Study Reference Manual.

Unexpected drug related SAEs as assessed by Sponsor or authorized person qualify for expedited reporting and will be reported to the IRB/EC, regulatory authorities, participating Investigators and, if cross reporting is required for SUSARs, in accordance with all applicable global laws and regulations. A SUSAR is a Serious Adverse Reaction, which is suspected to be caused by the investigational medicinal product and which is unexpected, ie, its nature or severity is not consistent with the information in the relevant Reference Safety Information. SAEs, including those that do not meet requirements for expedited reporting, and all other AEs will be reported to the regulatory agencies as appropriate.

9.10.3. Pregnancy

Any pregnancy, including the pregnancy of a male subject's female partner, that occurs during any phase of the study must be reported to the Sponsor or designated organization within 24 hours of learning of the pregnancy using a Clinical Study Pregnancy Form.

All study drugs should be discontinued, and the pregnancy should be followed to term. The details of termination must also be reported, including details of birth, the presence or absence of birth defects, congenital abnormalities or maternal and newborn complications, or whether termination was spontaneous or voluntary.

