3.3. Study Duration

Subjects will receive ALIS + background regimen or ELC + background regimen for 6 months and then remain off all study drugs for 1 month. The Screening period will be up to approximately -70 days to -1 day (~2.5 months).

The total duration of the study will be up to 9.5 months from the Screening visit to EOS.

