3.5. End of Study

The EOS is defined as the date of the last visit of the last subject.

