4.1.1. Inclusion Criteria

Subjects must satisfy all of the following criteria to be included in the study:

1. Male or female ≥ 18 years of age (19 years or older in South Korea)
2. Current diagnosis of MAC lung infection. MAC or mixed infection with MAC as the dominant species is allowed, with MAC as the intended organism for treatment
3. Positive sputum culture for MAC within 6 months prior to Screening
4. Positive sputum culture for MAC at Screening
5. A chest CT scan, read locally, within 6 months prior to Screening to determine presence and size of pulmonary cavities. Subjects who do not have a chest CT scan within 6 months prior to Screening will be required to obtain a chest CT scan, read locally, during Screening
6. In the Investigator's opinion, documented respiratory signs/symptoms at Screening that are attributable to the current MAC lung infection
7. An average QOL-B respiratory domain score of ≤ 85 based on scores at Screening and on the day of enrollment prior to randomization
8. In the Investigator's opinion, underlying lung disease (eg, COPD, bronchiectasis) have been managed according to best local standard of care, and on stable maintenance therapy for a minimum of 4 weeks prior to randomization
9. Willingness and ability to adhere to prescribed study treatment during the study
10. Ability to produce (spontaneously or with induction) approximately 2 mL of sputum for mycobacteriology at Screening
11. WOCBP (ie, fertile following menarche and until becoming post-menopausal unless permanently sterile) and fertile men (ie, all men after puberty unless permanently sterile by bilateral orchidectomy) agree to practice a highly effective method of birth control from Day 1 to at least 90 days after the last dose. Examples of such birth controls are:
 - true abstinence (refraining from heterosexual intercourse during the entire study),
 - copper IUD,
 - hormonal methods (levonorgestrel-releasing intrauterine system, progestogen implant, combined oral contraceptive pill [combined with barrier method]),
 - exclusive homosexual relationship, or
 - sole male partner who has undergone surgical sterilization with confirmation of azoospermia at least 3 months post procedure while participating in the study.
12. Provide signed informed consent prior to administration of study drugs or performing any study related procedure
13. Be able to comply with study drugs use, study visits, and study procedures as defined by the protocol

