4.2.3. Early Discontinuation Procedures

If a subject prematurely discontinues the study, the subject will do the following:

- Attend the EOT visit
- Attend EOS visit 28 days after the last dose of study drugs
- Complete EOS assessment

If a subject withdraws from the study, the Investigator will complete and report the observations as thoroughly as possible up to the date of withdrawal including the date of last treatment and the reason for withdrawal.

If the subject is discontinued from the study due to an AE, the Investigator will follow the subject until the Investigator deems that the AE has resolved or stabilized. In case of unresolved AEs including significant abnormal laboratory values at the EOS assessment, these events will be followed up until resolution or until they become stable.

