## 7.6. Derived and Transformed Data

### 7.6.1. Durations

A duration between one date (*date1*) and another later date (*date2*) is calculated using the following formula:

- Duration (days) =  $date2 - date1 + 1$
- Duration (weeks) = duration (days) / 7
- Duration (months) = duration (days) / 28
- Duration (years) = duration (days) / 365.25

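### If the study ends for each subject at Month 7/EOS, a pregnancy that begins in nominally the last 62 of the 90 post-dose contraception days need not be reported.

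*Protocol*

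**What the plan says.** Inclusion criterion 11 (Protocol 4.1.1) applies to women of child-bearing potential and fertile men. They must agree to a "highly effective method of birth control from Day 1 to at least 90 days after the last dose".

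Protocol 9.10.3 sets the reporting duty. A pregnancy, including one in a male subject's partner, "that occurs during any phase of the study must be reported to the Sponsor or designated organization within 24 hours". The clock runs from awareness: "within 24 hours of learning of the pregnancy using a Clinical Study Pregnancy Form". Reported pregnancies are followed to term and their outcome is recorded. No period after the last dose, or after the study, is named.

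When the study ends can be read in two ways:

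- **Per subject.** Protocol 3.3 says: "The total duration of the study will be up to 9.5 months from the Screening visit to EOS". Protocol 9.9 says: "The Investigator should proactively follow subjects with AEs until the EOS for each subject".
- **Study level.** Protocol 3.5 says: "The EOS is defined as the date of the last visit of the last subject".

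Subjects stop all study drugs at Month 6 and have their final visit at Month 7 (Protocol 3.1). Those who leave early are told: "Attend EOS visit 28 days after the last dose of study drugs" (Protocol 4.2.3).

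**The concern.** The contraception requirement treats conception within 90 days of the last dose as something to avoid. The reporting duty is tied to the study, not to the last dose, and a subject's visits end about a month after dosing. For most of the precaution period, a new pregnancy may therefore carry no reporting duty.

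Without a report, the follow-up to term and the recording of birth outcome in 9.10.3 never start. Scheduled pregnancy tests also stop at Month 7 (Protocol Table 4). Pregnancies conceived within the plan's own precaution period, and their outcomes, could then be missing from the safety record. Because the protocol uses end of study in two senses, sites could also apply the rule differently.

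**Working it through.** **Inputs**

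- Contraception after last dose: at least 90 days (Protocol 4.1.1, criterion 11).
- Last dose at Month 6, final visit at Month 7 (Protocol 3.1).
- Length of a month: "Duration (months) = duration (days) / 28" (SAP 7.6.1). Month 6 is Day 168 and Month 7 is Day 196.
- Screening: up to about 70 days (Protocol 3.3).
- Visit windows: 7 days either side (Protocol Table 4).

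**The plan's own figure.** The documents do not state the gap, but they do state the study duration per subject: 70/28 + 7 = 9.5 months. This matches Protocol 3.3, so that section counts a 28-day month and takes EOS as the subject's own Month 7.

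**Per-subject reading**

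Gap = max(0, 90 - (196 - last-dose day)) = max(0, last-dose day - 106)

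| Last dose of any study drug | Gap (days) |
|---|---|
| Day 168 (Month 6) | 62 (62/90 = 68.9%) |
| Day 140, stays to Month 7 | 34 |
| Day 112, stays to Month 7 | 6 |
| Day 106 or earlier, stays to Month 7 | 0 |

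A subject who leaves the study early, with EOS 28 days after the last dose, has 90 - 28 = 62 days.

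Sensitivity for a subject dosed to Month 6:

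- Month 7 visit moved within its window: 21 to 35 days off drug, so 69 to 55 days (76.7% to 61.1%).
- Month 6 and Month 7 visits moved in opposite directions: 14 to 42 days off drug, so 76 to 48 days.
- A calendar month of 30 to 31 days: 60 to 59 days.

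**Study-level reading**

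Let d be the days from a subject's Month 7 visit to the last subject's last visit. For a subject dosed to Month 6, gap = max(0, 62 - d): 62 days at d = 0, 32 at d = 30, and 0 at d = 62 or more.

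The documents give no enrolment duration. As an assumption, spread Month 7 visits evenly over L days, with every subject dosed to Month 6:

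- Share affected = 62/L: 62/365 = 17.0% for 12 months; 62/730 = 8.5% for 24 months.
- Mean gap over all subjects = 62²/(2L): 3844/730 = 5.3 days for 12 months; 3844/1460 = 2.6 days for 24 months.

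**Does other text close the gap?** Protocol 9.11 requires prompt notification after discharge, without time limit, but only of SAEs that the investigator considers reasonably related. A birth defect is an SAE under 9.9.2 and would qualify if judged related. A pregnancy is not in itself an SAE, so an uncomplicated one, or an outcome judged unrelated, falls outside 9.11.

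**The case against.** The strongest reply is that contraception and reporting are separate duties, and nothing in the documents says they must last equally long. The treatment-emergent adverse event window also closes 28 days after treatment (Protocol 9.9.1), so ending pregnancy reporting at about that point is coherent. This stands, and it is why the point is a suggested improvement.

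Second, the only express definition of end of study is the study-level one in Protocol 3.5. Under the enrolment assumption above, it leaves about 83% to 92% of subjects with no gap. This also stands as a limit on size. It does not remove the problem: the latest subjects remain uncovered, and cover depends on when a person happened to enrol. The 9.5-month arithmetic and the wording of 9.9 support the per-subject reading.

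Third, much is already covered. A pregnancy that begins before study end but is learned of later is reportable, because the duty turns on when the pregnancy occurs. Related SAEs are covered after discharge. What remains is mainly uncomplicated pregnancies and outcomes judged unrelated.

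Fourth, the Clinical Study Pregnancy Form, the Study Reference Manual and the consent form were not available. Any of them might already ask for later pregnancies.

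Finally, the consequence for the analyses is nil: SAP 12.13 only lists pregnancy test results.

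**Conclusion.** The point holds as a minor gap in safety capture. On the per-subject reading, 62 of the 90 days after the last dose carry no duty to report a new pregnancy. That figure assumes a last dose at Month 6, 28-day months and the 90-day minimum. On the study-level reading, the gap runs from 62 days for the last subject down to none for anyone whose Month 7 visit was at least 62 days before study end.

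These are calendar days; the documents give no basis for a count of pregnancies, which is likely to be very small. The primary objective and the planned analyses are unaffected. Confidence is medium because the size depends on which meaning of study end applies and on documents that could not be seen.

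**What to change.** In Protocol 9.10.3, extend the reporting duty beyond the study phases with wording such as: *and any subject or partner pregnancy that occurs up to 90 days after the last dose of any study drug*. Keep the same form and the same 24 hours from awareness. At the Month 7/EOS visit, ask subjects to tell the site of any such pregnancy. Tying the period to the last dose works under either meaning of study end.

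The cost is one sentence and one instruction at an existing visit, with no new visit or form. Capture after EOS would be passive, so it would find only pregnancies the site is told about. Sites may have a few more reports to file and follow to term. If the pregnancy form or the reference manual already asks for these reports, the change only brings the protocol into line.
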